10.2 Training of Staff

Prior to the screening of the first subject, an Investigator Meeting/Study Initiation Visit will be held. During this meeting/visit, the Sponsor or its authorized representative will discuss the requirements of the clinical study protocol and related documents and will also provide training to the relevant systems and other study-specific procedures. The activities of this meeting/visit will be described in the monitoring plan.

Confidentiality Statement

Data and information contained in this document are considered to constitute trade secrets and confidential commercial information, and the legal protections provided to such trade secrets and confidential information are hereby claimed under the provisions of applicable law. No part of this document may be publicly disclosed without the written consent of Philip Morris Products S.A.

Further to the Site Initiation Visit, the Investigator or designee will ensure that appropriate training relevant to the study is regularly provided to all staff involved in the study, and that any new information relevant to the performance of this study is forwarded in a timely manner to the staff. The Investigator or designee will maintain a record of all individuals involved in the study.

10.3 Audits and Inspections

Good Clinical Practice regulations require independent inspections of clinical program activities. Such inspections may be performed at any time before, during and/or after the study.

Authorized representatives of the Sponsor, regulatory agencies and/or IRB may perform audits or inspections, including source data verification. The purpose of an audit or inspection is to systematically and independently examine all study-related activities and documents to determine whether these activities were conducted, and data was recorded, analyzed, and accurately reported according to the protocol, ICH GCP guidelines and any applicable regulatory requirements. The Investigator or designee will contact the Sponsor or the authorized representative immediately if contacted by a regulatory agency about an inspection at their investigational site.

The Investigator and study staff are responsible for maintaining a comprehensive and accurate filing system of all study-related documentation that will be suitable for inspection at any time by the Sponsor, its authorized representative and/or regulatory agencies. By signing this protocol, the Investigator or designee understands and agrees to provide access to the necessary documentation and files.

Confidentiality Statement

Data and information contained in this document are considered to constitute trade secrets and confidential commercial information, and the legal protections provided to such trade secrets and confidential information are hereby claimed under the provisions of applicable law. No part of this document may be publicly disclosed without the written consent of Philip Morris Products S.A.

11 DATA MANAGEMENT ACTIVITIES

All data management activities will be described in detail in the data management plan (DMP) and documents specified therein.

11.1 Data Capture

11.1.1 Case Report Forms and Study Records

CRFs are produced by the CRO responsible for Data Management activities (DM-CRO), stored electronically, and are available to the designated study team members. Each CRF is reviewed and signed by the Investigator. The final signed CRFs are provided to the Sponsor in the format as decided upon between DM-CRO and the Sponsor (e.g., CD, flash drive, SFTP). This will be documented in the DMP). The subject questionnaires will be completed directly by the subject. Trained study personnel will be responsible for capturing the data from the observations, tests, and assessments specified in the protocol in the source documents and DM-CRO will enter the data into the CRF, in accordance with the CRF Completion Guidelines.

The Investigator has ultimate responsibility for the collection and reporting of all data related to the clinical study and ensuring that the data are accurate, authentic/original, legible, timely (contemporaneous), enduring, and available when required. The CRF must be signed by the Investigator to attest that the data contained in the CRF are true and accurate. Any correction made to source documents must be clearly recorded, without obscuring the original values and be accompanied by the date of change, reason for change, and identification of the person making the change. The CRF for each subject will be checked against the source documents at the investigational site by the Monitor. Instances of missing or unclear data will be discussed with the Investigator for resolution. A CRF will be generated for all subjects that sign the ICF.

11.1.2 Protocol Deviations

Protocol deviations are defined as any departure from the procedures defined in this document, including, but not limited to, any violation of inclusion/exclusion criteria, mis-randomization, use of any nicotine or tobacco-containing product other than the assigned product during the exposure period, assessments not performed or performed outside the scheduled time windows, or use of medications that are known to affect study endpoints.

Protocol deviations will be entered into the clinical trial management system (CTMS) or other approved format. The data collected in the CRF may be used to assess protocol deviations from the data programmatically. Protocol deviations will be reconciled and categorized prior to locking the clinical database as described in the DMP.

Confidentiality Statement

Data and information contained in this document are considered to constitute trade secrets and confidential commercial information, and the legal protections provided to such trade secrets and confidential information are hereby claimed under the provisions of applicable law. No part of this document may be publicly disclosed without the written consent of Philip Morris Products S.A.

Information from the source documents will represent the primary source of protocol deviations. Information following investigational site monitoring and other manual reviews will be documented in the investigational site visit reports, follow-up letters, audit documentation, or other manual review and will be recorded and tracked in the CTMS or other approved format. Telecommunications and other verbal communications regarding deviations will be considered and handled as important communication, documented and tracked as protocol deviations, as necessary.

Individual entries for protocol deviations that are recorded in the CTMS, or other approved format, following investigational site monitoring and other manual reviews, will be reviewed against the individual data points in the database. The overall procedure for managing protocol deviations are defined in the SOPs and study specific procedures of the DM-CRO. All deviations will be reviewed, as defined at study start, to identify trends to improve monitoring and/or potential impact on the statistical analysis.

11.2 Data Handling

All study data will be managed by the DM-CRO. The overall procedures for quality assurance of clinical study data are described in the SOPs of the DM-CRO. The DM-CRO will prepare the DMP that will be approved by the Sponsor, prior to the start of the study, i.e., First Subject Screened. This document will describe, in detail, the procedures and processes related to data management.

All data of all subjects that are enrolled will be captured and stored in the study database. For screen failures, only the following information should be captured: date/time of ICF signature, date of birth, sex, race, AEs, date and reason for screen failure.

All data collected during the study is property of the Sponsor, irrespective of the location of the database and the DM-CRO.

The sponsor should ensure that the Investigator has control of and continuous access to the CRF data reported to the sponsor. The sponsor should not have exclusive control of those data.

The Investigator should have control of all essential documents and records generated by the Investigator/observational site before, during and after the study.

Additional details are covered in the DMP.

11.2.1 Data Verification

The data will be verified as defined in the DMP and data validation plan (DVP). Data clarification forms (DCFs) will be issued to the observational site for discrepant or missing data.

Confidentiality Statement

Data and information contained in this document are considered to constitute trade secrets and confidential commercial information, and the legal protections provided to such trade secrets and confidential information are hereby claimed under the provisions of applicable law. No part of this document may be publicly disclosed without the written consent of Philip Morris Products S.A.

All changes to data will be captured in the database with a comprehensive audit trail.

11.2.2 Coding

Adverse events, concomitant diseases, medical/surgical history, prior/concomitant medication will be classified according to the terminology of the latest version of the following dictionaries, at time of coding the first entry:

Adverse events, concomitant disease, medical/surgical history: Medical Dictionary for Regulatory Activities (MedDRA®)

Prior/concomitant medication: WHO Drug Dictionary Enhanced and Anatomical Therapeutic and Chemical classification system

11.2.3 Database Lock

When all outstanding data management issues have been resolved and all validation, quality review and cleaning activities are complete as defined in the DMP, the Sponsor organizes a data review and ensures that the resolution of all raised queries and quality control of the changed data are performed by the CRO before approving the database locked.

Any changes to the database after that time can only be made by written agreement between the Sponsor and the data management and statistical teams at the CRO. Any changes must be documented in the database log file and if these impact the study analysis the PMP process for a database unlock may be requested.

The study database will be transformed into a Clinical Data Interchange Standards Consortium (CDISC) compliant format and transferred to the Sponsor as specified in the DMP and defined in the data transfer agreement. The clinical data will adhere to the CDISC Study Data Tabulation Model (SDTM) Data Structure Specifications.

Confidentiality Statement

Data and information contained in this document are considered to constitute trade secrets and confidential commercial information, and the legal protections provided to such trade secrets and confidential information are hereby claimed under the provisions of applicable law. No part of this document may be publicly disclosed without the written consent of Philip Morris Products S.A.

12 PLANNED STATISTICAL METHODS

12.1 General Considerations

Full details of the statistical analysis will be given in the Statistical Analysis Plan (SAP). The following statistical analyses will not be performed prior to the finalization of the SAP. Any changes to the planned statistical methods from the SAP will be documented in the clinical study report (CSR). The statistical evaluation will be performed using SAS[®], version 9.2 or later.

12.1.1 Stratification Criteria

The sample enrollment will enforce at least 40% of each sex, therefore analyses will be stratified by sex, as well as unstratified, as detailed in the SAP.

12.1.2 Definitions for Statistical Data Analysis

For PK and PD analyses, baseline will be defined as the last assessment prior to T₀ (5 minutes prior to T₀) for each study day of exposure.

Nicotine PK parameters (e.g., T_{max}, C_{max}, AUC_{0-T_{max}}) will be derived from background-corrected nicotine concentrations.

12.1.3 Descriptive Statistics

All data will be presented in listings, ordered by subject, study visit, product, and time point, unless otherwise specified.

Continuous endpoints will be summarized with descriptive statistics including number of subjects (n), number and percent of subjects with missing data, arithmetic means and standard deviations (mean and SD), median, first and third quartiles, minimum and maximum.

For log normally distributed endpoints, geometric mean, geometric CV, and confidence interval will be presented additionally.

Nominal categorical variables will be summarized by frequency statistics (number and percentage), including the number of missing data as a category.

Ordinal categorical data (e.g., T_{max}) will be summarized by number of subjects (n), number and percent of subjects with missing data, median, first and third quartiles, and minimum and maximum.

For PK and PD endpoints, all analyses and summaries will be performed by product.

Confidentiality Statement

Data and information contained in this document are considered to constitute trade secrets and confidential commercial information, and the legal protections provided to such trade secrets and confidential information are hereby claimed under the provisions of applicable law. No part of this document may be publicly disclosed without the written consent of Philip Morris Products S.A.

For safety endpoints, analyses and summaries will be performed by product and sequence, and overall.

12.1.4 Handling of Missing Values and of Values outside the Detection Limits

In general, missing data will not be imputed in this study, due to the nature of the measurements and the short periods of exposure and use. However, for questionnaire data, total scores and domain or subscale scores may use a certain degree of imputation by averaging across individual item scores. Further details will be provided in the SAP.

In general, bioanalytical values below the lower limit of quantification (LLOQ) will be imputed using $0.5 \times$ lower limit of quantification. For values above the upper limit of quantification (ULOQ), the ULOQ will be used for calculation and reporting in summary tables.

For nicotine concentrations below the LLOQ (BLOQ):

- BLOQ values before T0 will be imputed by LLOQ/2.
- BLOQ values after the last quantifiable value are not included in the analysis (e.g., for the calculation of AUC).
- Any BLOQ value (after T0 and before the last quantifiable value) would need to be queried and, if confirmed, it will be imputed by LLOQ/2.

The number and percent of values below LLOQ or above ULOQ will be presented in each summary table.

12.1.5 Significance Level for Inferential Analysis

Not applicable.

12.2 Determination of Sample Size and Power Consideration

In this study 36 subjects will be randomized to 6 product use sequences. This sample size is empirically based as there are no considerations for statistical hypothesis.

In an analysis of confidence interval precision on the P4M3 Gen 2.0: cigarettes C_{max} ratios, performed with SAS with 10,000 simulations,

- The precision has been determined to be of 0.55, and
- The geometric coefficient of variation (GCV) has been determined to be of 50%.

Confidentiality Statement

Data and information contained in this document are considered to constitute trade secrets and confidential commercial information, and the legal protections provided to such trade secrets and confidential information are hereby claimed under the provisions of applicable law. No part of this document may be publicly disclosed without the written consent of Philip Morris Products S.A.

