A mixed model analysis of variance (ANOVA) will be conducted on AUC_{0-2min} , AUC_{0-4min} , AUC_{0-Tmax} , AUC_{0-10h} , AUC_{0-last} , $AUC_{0-infinity}$, $\max(C_t/t)_{t \in [0, T_{max}]}$ and C_{max} endpoints in the natural logarithmic scale. The results of this analysis will be presented in terms of geometric least square mean ratios and 95% confidence intervals (95% CI) for the P4M3 Gen 2.0: cigarettes ratio and the ratios of variants of P4M3 Gen 2.0.

Confidentiality Statement

Data and information contained in this document are considered to constitute trade secrets and confidential commercial information, and the legal protections provided to such trade secrets and confidential information are hereby claimed under the provisions of applicable law. No part of this document may be publicly disclosed without the written consent of Philip Morris Products S.A.

The analysis of T_{max} will be conducted using non-parametric tests and Hodges-Lehmann estimates of median difference with its derived 95% CI.

Sample Size:

The sample size is empirically based as there are no considerations for statistical hypothesis.

A total of 36 subjects is expected to be sufficient to obtain a precision of 0.55 or less on the P4M3 Gen 2.0 : cigarettes C_{max} ratios.

Confidentiality Statement

Data and information contained in this document are considered to constitute trade secrets and confidential commercial information, and the legal protections provided to such trade secrets and confidential information are hereby claimed under the provisions of applicable law. No part of this document may be publicly disclosed without the written consent of Philip Morris Products S.A.

TABLE OF CONTENTS

1	ETHICS AND REGULATIONS	24
1.1	Independent Review Board (IRB) Approval	24
1.2	Ethical Conduct of the Study	25
1.3	Subject Information and Consent.....	25
1.3.1	Informed Consent Form for Study Participation	25
1.3.2	Amendment to the Informed Consent Form	25
1.4	Good Clinical Practice and Regulatory Requirements	26
2	INTRODUCTION	27
2.1	Background.....	27
2.1.1	Smoking-Related Diseases and Harm Reduction Strategy	27
2.1.2	Description of the Product and Scientific Findings	28
2.2	Purpose of the Study	29
2.3	Anticipated Benefits and Risks.....	29
2.3.1	Anticipated Benefits.....	29
2.3.2	Anticipated Foreseeable Risks due to Study Procedures	29
2.3.3	Anticipated Foreseeable Risks due to Investigational Product.....	29
2.3.4	Unforeseeable Risks.....	30
3	STUDY OBJECTIVES.....	31

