12.2.1 Assumptions

The precision has been determined using the following geometric mean (GM), geometric coefficient of variation (GCV) and within subjects correlation assumptions for C_{max} :

- For all products the GCV is 80% (in previous study [5] GCV is in the range of 0.63 to 0.83)
- For usual brand of cigarettes, the GM is 12 ng/mL (in previous studies [32-34] this GM is in the range of 11 to 13)
- For P4M3 Gen 2.0 variants with 3.5% nicotine, the GM is 11 ng/mL (in previous a previous study [5] GM is in the range of 9.4 to 12)
- The correlation within subjects on log-transformed data is 0.8 (in previous studies [32-34] this correlation is in the range of 0.82 to 0.88)

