12.2.2 Method

The analysis of confidence interval precision on the P4M3 Gen 2.0: cigarettes C_{max} ratios has been implemented using SAS, simulating 10000 sets of log-transformed data for 36 subjects with the assumptions described in section 12.2.1, the 3 periods and the 6 sequences of this cross-over design.

The statistical analysis has been performed with a linear model with repeated measurement including as fixed effect the sequence, the period, and the product exposure.

The P4M3 Gen 2.0:cigarettes C_{max} ratios and related confidence intervals have been determined by using the exponential of the difference between P4M3 Gen 2.0 variants and cigarettes on the log-transformed data.

Then precision has been determined as the 90th percentile of the 95% confidence interval of the P4M3 Gen 2.0: cigarettes C_{max} ratios.

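### The stated C_max-ratio precision of 0.55 for 36 subjects does not follow from the protocol's own inputs, which give a 95% CI width of about 0.31, and the accompanying 50% GCV is undefined

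*Protocol*

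**What the plan says.** Protocol Section 12.2 gives two simulation results for the P4M3 Gen 2.0:cigarettes C_max ratio. The first reads "The precision has been determined to be of 0.55, and"; the second, listed as a separate item, reads "The geometric coefficient of variation (GCV) has been determined to be of 50" percent. The synopsis turns the first into a bound: "36 subjects is expected to be sufficient to obtain a precision of 0.55 or less". The number of subjects is not tied to a test: "This sample size is empirically based as there are no considerations for statistical hypothesis".

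Section 12.2.1 lists the inputs:
- "For all products the GCV is 80% (in previous study [5] GCV is in the range of 0.63 to 0.83";
- a geometric mean of 12 ng/mL for cigarettes (earlier studies 11 to 13) and 11 ng/mL for the 3.5% variants (9.4 to 12 in an earlier study);
- "The correlation within subjects on log-transformed data is 0.8 (in previous studies [32-34] this correlation is in the range of 0.82 to 0.88".

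Section 12.2.2 describes the method as "simulating 10000 sets of log-transformed data for 36 subjects with the assumptions described in section 12.2.1", in 3 periods and 6 sequences. The analysis is a repeated-measures linear model with sequence, period and product as fixed effects, and "precision has been determined as the 90th percentile of the 95% confidence interval" of the ratio. The SAP text has no sample-size section that adds to this.

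**The concern.** Every input needed to check the figure is printed next to it, yet the figure looks too large for them. A within-subject correlation of 0.8 removes most of the 80% variability from a within-subject contrast, so 36 subjects should give an interval much narrower than 0.55. A GCV of 50% is also reported as a finding, when the only GCV among the assumptions is 80%.

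This is the plan's only quantitative statement of what 36 subjects will deliver. If it cannot be reproduced, either the result is misreported or the listed assumptions are not those that were simulated. In the second case, a reader who relies on Section 12.2.1 would misjudge the variability the sponsor expects.

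**Working it through.** **Inputs.** N = 36, 3 periods, 6 sequences (12.2, 12.2.2). GCV 80%, log-scale correlation 0.8, geometric means 12 and 11 (12.2.1). Two-sided 95% CI, 90th percentile over 10,000 data sets (12.2.2). One GCV and one correlation for all products imply compound symmetry. Sequence and period effects are fitted, so whatever values were simulated for them do not affect the width.

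**Closed form.**
1. Total log variance = ln(1 + 0.8²) = 0.4947 (SD 0.7033).
2. Within-subject variance = (1 − 0.8) × 0.4947 = 0.0989.
3. SE of the log ratio = √(2 × 0.0989 / 36) = 0.0741.
4. Residual df = 108 − 36 − 2 − 2 = 68, so t = 1.995 and the log half-width = 1.995 × 0.0741 = 0.148.
5. Ratio = 11/12 = 0.917, so the CI = 0.917 × e^(±0.148) = 0.79 to 1.06, a width of 0.27.

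**Simulation of the Section 12.2.2 method (10,000 trials).** The median width was 0.27 and the 90th percentile 0.313. The maximum was 0.40 to 0.42 depending on the seed, and no trial reached 0.55. The stated value is 0.55 / 0.313 ≈ 1.8 times the recomputed one.

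**Other readings of precision, 90th percentile.**

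| Reading | Value |
|---|---|
| Full width | 0.31 |
| Half-width | 0.16 |
| Width on the log scale | 0.33 |
| Upper limit / lower limit | 1.39 |
| Upper limit | 1.17 |
| Lower limit | 0.87 |

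**Other choices of model or input, 90th-percentile full width.**

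| Change | Width |
|---|---|
| Contrast-specific (paired) variance | 0.33 |
| Wider of the two variants' CIs | 0.32 |
| 80% taken as the log-scale SD | 0.36 |
| 99% instead of 95% CI | 0.42 |
| 50% taken as the within-subject GCV | 0.49 (0.51 paired) |
| Correlation ignored | 0.78 |

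**Cited ranges.** These were GCV 63% to 83%, correlation from the assumed 0.80 to the cited maximum of 0.88, and mean ratio 9.4/13 = 0.72 to 12/11 = 1.09. The width runs from 0.153 (63%, 0.88, 0.72) to 0.385 (83%, 0.80, 1.09). With the lowest cited correlation, 0.82, the top value is 0.363.

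**Back-solving, for scale only.** A full width of 0.55 at N = 36 would need a correlation near 0.44 at GCV 80%, or a GCV near 170% at correlation 0.8. With all other inputs kept, it would correspond to about 14 to 15 subjects.

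**The 50% GCV.** The inputs imply an intra-subject CV of √(e^0.0989 − 1) = 32.2%. For the individual product:cigarettes ratio, the GCV is √(e^(2 × 0.0989) − 1) = 46.8%, with a 90th percentile near 52% across simulations. The second is close to 50%, but the protocol does not say that this is the quantity meant.

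**The case against.** The best defence is that little depends on the number. The sample size is declared empirical, and there is no hypothesis, margin or success criterion. The synopsis states a bound that 0.31 meets, and by the same calculation about 15 evaluable subjects would still meet it, so dropouts or exclusions would not readily break it. All of that stands, and for that reason the point does not question N = 36. It does not rescue Section 12.2, which gives 0.55 as the determined value and not as a ceiling.

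A second objection is that 0.31 itself rests on choices the text leaves open. Section 12.2.2 does not say width, and it names no covariance structure; the analysis model in SAP Section 6.5.1 uses heterogeneous compound symmetry with Kenward-Roger degrees of freedom. This is fair, but a contrast-specific variance moves the full width only to about 0.33, and the other readings of precision also miss 0.55.

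Third, causes other than wrong inputs are possible. The 90th percentile of the ratio's GCV under a paired analysis is about 0.55 (0.546), so an output may have been mislabelled. This is speculation that only the code can settle. It is a reason to check the code before replacing any number.

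Finally, the 50% GCV is a gap in labelling and would be minor on its own.

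**Conclusion.** The point holds. With the inputs and method in Sections 12.2.1 and 12.2.2, the 90th-percentile 95% CI width is 0.31 (0.33 with a contrast-specific variance), against a stated 0.55. The result assumes 36 evaluable subjects, lognormal C_max with one GCV and one correlation for all products, and precision read as full width; read as half-width, the gap is larger. The documents do not show whether the 0.55 or the list of inputs is wrong.

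If the listed inputs were simulated, the error is conservative: 36 subjects do better than claimed and the synopsis bound holds loosely. If 0.55 is a correct full width, Section 12.2.1 does not describe what was simulated, and a reader using it would expect intervals a little over half as wide (0.31/0.55 ≈ 0.57) as the sponsor does. Either way, the sample size, design and analysis are unaffected. The statement should still be corrected, because it is the plan's only account of what the sample size achieves.

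**What to change.** 1. Check the simulation code against Section 12.2.1.
2. In Section 12.2.2, state whether precision is the full width or the half-width of the 95% CI of the ratio, and name the covariance structure fitted.
3. If the listed inputs were used, replace 0.55 in Section 12.2 and the synopsis with the value from the code, expected to be about 0.31 for full width (0.33 with a contrast-specific variance) or 0.16 for half-width. If other inputs produced 0.55, list them in Section 12.2.1 with their source.
4. Say which quantity the 50% GCV describes; if it is the individual product:cigarettes ratio, the listed inputs give about 47%.

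The cost is a check of existing code and a few lines of text. N stays at 36, and neither the design nor the analysis changes.
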